13.0 Provisions to Monitor the Data to Ensure the Safety of Subjects

A. Creation of a Data and Safety Monitoring Board (DSMB): We will have a Data and Safety Monitoring Committee (DSMC) in place. Two of the members of the DSMB are physician scientists external to MUSC well known in the field of neonatology and nutrition. [name], MD a neonatologist at Yale University, and [name], MD, a neonatologist at Rainbow Babies and Children's Hospital. One member will be a biostatistician at MUSC. He will maintain the database of the study, follow

HIPAA guidelines, and conduct ongoing interim analyses to ensure that the risk: benefit analyses remain in favor of benefit to the subjects.

B. Conduct ongoing monitoring of interventional trial by those who have appropriate expertise to accomplish the trial's mission: The PI will be responsible for checking laboratories of the women within 24 hours of their reporting and then entering the laboratory data into the computer. She will be provided with a set of normative laboratory values as a reference. The PI will review values weekly or will be notified if a value falls outside of the referent value range. All data will be verified independently by *[name], MA. The DSMB will be notified via email with source documents and adverse report sheets if a subject's value falls outside the referent value range. In addition, all adverse events will be reviewed quarterly by the DSMC, whose report will be forwarded to the IRB on a quarterly basis. The Investigators will report all Serious Adverse Events by email to the IRB and the DSMC; in addition, the IRB will receive a email report within 10 days of the Clinical Investigators' knowledge of the Event. In addition, the investigators will generate a quarterly report to the DSMC regarding subject enrollment, subject completion, adverse events and serious adverse events. The DSMC will review the report and a summary letter with their findings sent to the IRB.*

C. Interim Data Analyses & Monitoring: Interim analyses for the evaluation of safety and efficacy will be conducted based on the recommendations of the Data Safety & Monitoring Board for two reasons: more than 10% of subjects in a given arm had achieved urinary calcium/creatinine ratios outside the acceptable range or there is evidence to the DSMC that there is significant clinical benefit to a given treatment arm over the other arm or arms of the study. The DSMC will serve to monitor for safety and efficacy. DSMB reports will include summary statistics: on mother-child recruitment (expected vs. actual); mother-child follow-up visits (expected vs. actual); data form quality (completion and timeliness of forms); tracking of data editing; demographics of the randomized mothers-children; aggregate safety; aggregate efficacy; and related information. The DSMB also will monitor the trial from the standpoint of futility using the techniques of Lan and Wittes (43).

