12.0 Data Management

All maternal and infant blood and urine samples obtained will be labeled with the patient's name, subject ID number, and medical record number to ensure proper tracking. Each study subject and her infant then will be assigned a specific study number without any reference to the woman or infant's name, which will be used to enter all data into RedCap. We will follow all HIPAA guidelines to maintain protection of patient/subject information. With these precautions in place, there is a remote risk that the samples and data could be linked to the woman and her infant; however, the study number and the name will be kept in a separate file in the locked office of [name]. The data will be entered into a secured database with only the study number entered, thus ensuring that the number and data will be kept separately from the woman and infant's names.

- *Describe the data analysis plan, including any statistical procedures.*

Power Analysis

Treatment Group	V1 [p= 0.03]	V4 [p<0.001]	V1 SD	V4 SD	n	Cohen's D	f
400 IU Vit D/day Mother & Infant Placebo Group	86.5	80.2	31.42	28.19	74	1.668	0.834
6400 IU Vit D/day Mother & Infant Group	98.6	149	35.31	45.88	74		

F tests - ANOVA: Repeated measures, within-between interaction based on effect size calculated from figure above.

Analysis: *A priori*: Compute required sample size

Input: Effect size $f = 0.834$

α err prob = 0.05

Power (1- β err prob) = 0.80

Number of groups = 2

Number of measurements

Corr among rep measures = 0.5

Nonsphericity correction $\varepsilon = 1$

Noncentrality parameter $\lambda = 2$

Critical F = 4.4589701

Output: Noncentrality parameter $\lambda = 25.0400160$

Critical F = 4.4589701

Numerator df = 2.0000000

Denominator df = 8.0000000

Total sample size = 6 (3 per gr)

Actual power = 0.9620629

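### Protocol Section 13.0 opens an interim efficacy analysis once benefit of one arm has already been seen, and also on a urinary safety signal, so the data would set the timing of efficacy looks

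*Protocol*

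**What the plan says.** Protocol Section 13.0, part C, states that interim analyses evaluating both safety and efficacy are done on the monitoring committee's recommendation, for either of two reasons:

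- **Safety signal:** "more than 10% of subjects in a given arm had achieved urinary calcium/creatinine ratios outside the acceptable range".
- **Benefit signal:** "there is evidence to the DSMC that there is significant clinical benefit to a given treatment arm over the other arm or arms".

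The same part lists efficacy in aggregate among the items in the committee's reports, without saying whether that means pooled or by arm. It adds that the committee "will monitor the trial from the standpoint of futility", citing the Lan and Wittes technique. No sequential method is named for efficacy.

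Part A says that the biostatistician member will "conduct ongoing interim analyses to ensure that the risk: benefit analyses remain in favor of benefit to the subjects". No number or timing is given. The quarterly report described in part B covers enrolment, completion, adverse events and serious adverse events, not efficacy.

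Alpha appears once, in the power analysis in Section 12.0 ("α err prob = 0.05"), as an input to a sample-size calculation. Section 6.0 sets the size at 50 dyads, 25 per group, and calls the study an initial pilot.

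**The concern.** The benefit trigger puts the conclusion before the analysis. The committee can hold evidence that one arm is better only if someone has already compared the arms. The efficacy analysis is then opened because that comparison was favourable.

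Spending functions allow flexible timing of looks, but only if the timing does not depend on the observed treatment difference. Their error calculation treats each look as taken at a time chosen without regard to the current value of the statistic. A look called because the difference is large breaks that condition, so a boundary added later in an SAP or charter would not repair this sentence.

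The safety trigger has a milder version of the problem. A question about urinary calcium gives the committee a reason to open efficacy data, which adds unplanned efficacy looks.

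If the committee acted on such looks, the false-positive rate could exceed the nominal level, and an effect estimated at a favourable moment would tend to be too large. This pilot's estimates could feed the planning of a later trial.

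**Working it through.** **1. The protocol's own figure, and the role of 0.05.** Inputs from Section 12.0: f = 0.834, 2 groups, correlation 0.5, N = 6, alpha 0.05. The number of measurements is blank in the text as available; the numerator df of 2 with 2 groups implies m = 3.

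- λ = f² × N × m / (1 − ρ) = 0.695556 × 6 × 3 / 0.5 = 25.040016
- df = (2 − 1)(3 − 1) = 2 and (6 − 2)(3 − 1) = 8; critical F = 4.4589701
- Power from the noncentral F = 0.9620629

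All of these match Section 12.0. The calculation assumes one analysis. It shows that 0.05 is a sample-size input; nothing in it makes 0.05 the level of an interim test.

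**2. The benefit trigger under each reading of the reports.** If the aggregate efficacy in the committee's reports is pooled over arms, those reports cannot show whether the trigger has been met. If it is by arm, efficacy looks occur before the analysis that is meant to be the look. The sentence needs changing either way.

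**3. The urinary trigger in small numbers.** One subject of nine is 1/9 = 11.1%, above 10%; one of ten is exactly 10% and does not exceed it. So a single subject meets the criterion while an arm has nine or fewer. At 25 per arm it takes three (3/25 = 12%; 2/25 = 8%). Meeting it allows the committee to recommend an analysis; it does not force one.

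**4. Illustration of what unadjusted efficacy looks would cost.** Assumptions, none of them in the protocol: K equally spaced looks including the final one, each at two-sided 0.05, success at the first crossing, no true difference. Then

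α(K) = 1 − P(|Z₁| < 1.96, …, |Z_K| < 1.96), with corr(Zᵢ, Zⱼ) = √(i/j) for i < j.

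| Looks K | z test | t test, 25 per arm at the final look |
|---|---|---|
| 1 | 5.0% | 5.1% (simulation error about 5%) |
| 2 | 8.3% | 8.4% |
| 3 | 10.7% | 10.9% |
| 4 | 12.6% | 13.1% |
| 5 | 14.2% | 14.5% |
| 6 | 15.5% | 16.2% |

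The z column is by numerical integration and agrees with simulation. The t column is simulated (100,000 runs). The extremes are 5% if no efficacy decision is taken at an interim, and about 24% (simulated 23.8%) if the t test is repeated after every added pair from three per arm onward.

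These are fixed, equally spaced looks. They show the cost of repeated unadjusted testing; they do not model looks timed by the observed effect.

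**5. Cost of a proper boundary.** With a Lan-DeMets O'Brien-Fleming-type function applied to each 0.025 tail at equal spacing, the final two-sided nominal level is about 0.049 with 2 looks and 0.044 with 4, and the overall level is held at 0.05.

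**The case against.** The strongest reply is that boundaries, alpha spending and the number of looks commonly belong in an SAP or charter, and an SAP may exist that is not at hand. That is right, and their absence from the protocol is not the point here. The reply does not reach the trigger itself, because the protocol states when an efficacy analysis is opened and makes that depend on the result.

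A reader might infer more than the document supports:

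- **That the trial's type I error is 8% to 15%.** This needs several looks, each at unadjusted 0.05, with success at the first crossing. The protocol states none of these. A committee that sees data does not by itself raise the error rate; an unadjusted decision rule does, and none is given.
- **That the analyses in part A are repeated efficacy tests.** They are described in terms of risk and benefit, under a heading on subject safety, so counting them as efficacy looks is not justified.
- **That the trigger means statistical significance.** The text speaks of significant clinical benefit, which need not be a p-value.
- **That the futility sentence is wrong.** It omits the outcome, the assumed effect and the cut-off, but an SAP may hold these. Any figure for how often futility would be declared rests on a cut-off that the protocol does not give.

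Having two primary outcomes is a separate multiplicity question and adds nothing to this point.

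**Conclusion.** The point holds as a defect of wording and design in Section 13.0, part C. The benefit trigger is circular and makes efficacy looks depend on the observed effect; the urinary trigger opens efficacy data without need; and the one sequential method named, being for futility, does not control the efficacy error rate.

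No type I error can be assigned to the plan as written. The figures of about 8% to 15% are conditional on 2 to 6 unadjusted looks with success at the first crossing. The defect in the trigger does not depend on them. For a pilot of this size it is worth correcting because the correction is easy, not because a particular inflation has been shown.

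**What to change.** In Section 13.0, part C:

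1. Delete the benefit trigger.
2. State that an analysis opened by the urinary calcium/creatinine trigger covers safety data only.
3. State that this 50-dyad pilot will not stop early for efficacy or claim success before the final analysis.
4. Say whether the efficacy summaries in the committee's reports are pooled or by arm.

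This costs a protocol wording change and no sample size; the final analysis keeps its full 0.05.

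If efficacy looks are wanted, replace step 3 with a schedule set by calendar time or by the number of dyads with 3-month data, independent of the observed difference. Name the outcome tested and use a Lan-DeMets O'Brien-Fleming-type spending function. The price is a final nominal two-sided level of about 0.049 with 2 looks or 0.044 with 4.

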14.0 Withdrawal of Subjects

- Describe anticipated circumstances under which subjects will be withdrawn from the research without their consent, including stopping participation for safety reasons.
 - Mother and infant move away from the study site
 - Infant is transferred to another facility
 - If mother had baseline hypercalcemia or hypercalciuria or baby had hypercalcemia, they would exit the study
- Describe any procedures for orderly termination of subjects by investigator.
 - The PI would notify the subjects in both writing and verbally if their participation is terminated.
- Describe procedures that will be followed when subjects voluntarily withdraw from the research, including partial withdrawal from procedures with continued data collection.
 - For voluntary withdrawal, the participant would notify the PI in writing. If mother requests to withdrawal either her or the infant, they will both be removed from the study without further data collection.

15 Risks to Subjects

1. The Risks of Phlebotomy:

- a. **Maternal:** The total amount of blood to be drawn at each maternal visit is 15 mL. Using aseptic technique, blood will be drawn monthly for a maximum of 4 blood draws (initial visit and monthly beginning at month 1 through month 3) during the study period and the total amount of blood over the study period will not exceed 60mL (<½ cup). Momentary discomfort may occur when skilled technicians or nurses perform phlebotomy with slight pain when the needle is inserted into a vein. Pressure will be applied to the arm following the procedure to minimize the risk of bruising; however, despite these efforts, a bruise may form at the site. Lastly, there is a slight chance of inflammation of the vein and/or blood clot formation, but this is extremely rare.
- b. **Infant:** The total amount of blood to be drawn during the study period (initial visit and months 1, 2, and 3) will be 2 mL at each visit (less than a teaspoon or less than 0.6% of the infant's total blood volume) or 10 mL (<2 tablespoons) over the course of 3 months. Using aseptic technique, blood will be drawn from the infant's hand, arm or heel either via venipuncture or heel stick. As with any blood draw, there may be a slight pain when the needle is inserted into a vein. Momentary discomfort may occur when skilled technicians or nurses perform phlebotomy. Pressure will be applied to the arm following the procedure to minimize the risk of bruising; however, despite these efforts, a bruise may form at the site. Lastly, there is a slight chance of inflammation of the vein and/or blood clot formation, but this is extremely rare.

2. The Risks of Randomization in the Study:

- a. There is a possibility that the treatment that each subject receives may prove to be less effective or to have more side effects than the other study treatment(s) or other available treatments. Because the ideal dose of vitamin D during lactation for mothers of preterm infants is unknown presently, the only way to determine the optimal dose is through a well-controlled, well designed scientific study that we are attempting to initiate.

3. The Risks of High Dose Maternal Vitamin D Supplementation are hypercalciuria and hypercalcemia.

hypercalciuria and hypercalcemia. There is a small risk that the woman's blood calcium level would increase in response to higher dose vitamin D supplementation. The body responds by excreting calcium in the urine to maintain normal calcium levels. If calcium levels in the blood continue to rise, then serum calcium will increase leading to hypercalcemia. This process takes weeks to months to occur. It takes approximately 3 months to reach steady state on an increased vitamin D intake/regimen. In related studies conducted at MUSC comparing maternal vitamin D supplementation with 400, 2400, or 6400 IU of vitamin D₃/day and their infants for 7 months, there were no differences in infant or maternal safety parameters (22). There were no reported episodes of either hypercalciuria or hypercalcemia in any of the treatment groups. In fact, maternal 25 (OH)D levels were higher in the 6400 IU/day treatment group compared to the 400 IU group. In breastfed infants, there was no statistical difference in the average circulating 25 (OH)D in either treatment arm (22).

- a. To ensure that each lactating mother and her breastfeeding infant and each nonlactating mother (and her formula-feeding infant as a control) maintain normal vitamin D status throughout the study period and not develop hypervitaminosis D, both mother and infant will be screened monthly for hypercalciuria, the first indicator of hypervitaminosis D. All study subjects will be monitored closely for hypervitaminosis D. Operationally, we define caution limits as urinary Ca/creatinine ratio > 0.8 mmol/mmol. Whenever any patient

exceeds the caution limit, a specific case study will be initiated by the Data Safety and Monitoring Committee (DSMC) to examine the contribution of sunlight exposure and other confounding factors. Operationally, we define upper limits as a urinary calcium/creatinine ratio > 1.0 mmol/mmol Ca/creatinine ratio. This is a conservative upper limit as circulating levels achieved in individuals living in sun-rich environments achieve this amount without causing toxicity. The DSMC will be convened to review any patient who exceeds any predefined toxic limit for any outcome. If the elevated levels are unexplained, the patient will be withdrawn from supplementation but will continue to be monitored.

4. **The Risk of Maternal Vitamin D Supplementation on the Infant:** The developing infant's vitamin D levels are 50% of maternal serum levels at birth and rise gradually over the next 2-3 months if there is adequate delivery or synthesis (by skin). Because mothers who are breastfeeding and who are deficient in vitamin D produce milk that is deficient in vitamin D, there is a need to supplement either the infant directly or the mother herself. This study is designed to increase maternal circulating 25(OH)D levels of lactating women through the use of high dose supplementation. Approximately ~20% of maternal vitamin D passes into the milk, and therefore, the risk of hypervitaminosis D in infants whose mothers are receiving the 6,600 IU/day vitamin D₃ regimen—based on predicted maternal circulating 25(OH)D is extremely low (22). There is a risk of hypovitaminosis D to the infant whose mother is receiving the 600 IU/day D₃ regimen if that infant is not receiving the infant vitamin D₃ drops that are prescribed as part of that treatment arm (Group A).

Minimizing Risk of Hypovitaminosis D Identified by an Infant's Participation in this Study:

As an additional safety measure, if at visit 4, any infant in any treatment arm, circulating 25(OH)D concentration is found to be below normal [defined *a priori* as <20 ng/mL (<50 nmol/L)], will be supplemented with the 400 IU vitamin D/day. If an infant's circulating 25(OH)D concentration is <10 ng/mL (<25 nmol/L) and is associated with a serum calcium level of <7.5 mg/dL (<18.75 nmol/L) at 3 months or older, then compliance of mother with her prescribed vitamin D regimen and that of the infant will be assessed. If mother has been compliant with the prescribed infant vitamin D₃ supplementation and the infant continues to have evidence of vitamin D deficiency with hypocalcemia, the infant will be referred to their pediatrician for further evaluation.

5. **The Risk of Milk Collection:** There is minimal physical risk in donating a milk sample either by using a manual or electric pump.
6. **The Risk of Breach of Confidentiality through Collection of Medical History and Clinical Laboratory Data:** As with any research study, there is a small risk that medical information, laboratory reports and data could become available to individuals outside of the study. All study personnel will adhere to HIPAA guidelines and regulations.
7. **The Risk of Measuring Degree of Skin Pigmentation using a skin tone chart and the Smart Probe 400,** a commercially available spectrometer, is minimal. The probe, from which a beam of visual spectrum light is emitted, and the absorbance measured, lightly touches the skin. Readout of the absorbance corresponds to the degree of pigmentation on a scale from 1 to 12. This technology is similar to what is currently used to measure bilirubin levels in neonates (transcutaneous bilirubin spectrometer) without any known side-effects. The information will be entered as a number into the database that will not be linked to the individual's name or medical record number such that confidentiality is maintained.

8. **The Risk of Postnatal Depression/Anxiety Screening:** The benefits of postnatal depression/anxiety screening far outweigh the risks. There is a risk that if the women are not screened for postpartum depression, they will not receive adequate evaluation and treatment. Asking questions about sadness and depression, anxiety and sleep problems can raise uncomfortable feelings that could precipitate suicidal ideation; however, any woman with clinical depression who goes without medical assessment and treatment is at greater risk. Studies have shown that early intervention has a positive impact on the outcome of the woman and her family.

Based on the EPDS screening tests, those women who score in the high range for anxiety and depression will be referred to their primary care provider or if having suicidal ideation, to the Emergency Department (as outlined below). Those women who qualify for further evaluation and treatment will receive both written and verbal information regarding postpartum depression and the ill effects it can produce for themselves, their infant and other family members. Women will be referred to therapists at MUSC who specialize in postpartum depression. Any woman responding positively to the suicidal questions will be escorted to MUSC's Emergency Department for further evaluation and treatment.

9. **Unknown Risks:** The experimental treatments may have unknown side-effects that previously have not been reported (unexpected and unanticipated adverse events or effects).

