4.0 Study Endpoints

- Primary outcomes will be:
 - Infant total circulating 25(OH)D concentration at 3 months
 - Mother total circulating 25(OH)D concentration at 3 months
- Primary or secondary safety endpoints
 - Maternal serum calcium concentration initially and at months 1-, 2-, and 3
 - Maternal urine calcium/creatinine ratios initially and at months 1-, 2-, and 3
 - Infant serum calcium concentration at time points initially and at months 1-, 2-, and 3

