7.0 Setting

Mothers and their infants will be initially seen in the MUSC Shawn Jenkins Children's Hospital NICU. If still inpatient for the remainder of their 2-3 visits, they will continue to be seen there. Following discharge, study visits will either be conducted in infant High-Risk Clinic or the Research Nexus clinic (MUSC Clinical Sciences Building, suite 214). The infant High-Risk Clinic has exam rooms, registration personnel and nursing staff. The NEXUS outpatient clinic has exam rooms, nursing staff, registration staff and lab personnel. We will meet the subjects at any of these sites and conduct the visits. There is only potential for 3 outpatient visits.

[figure not shown]

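### Section 14.0 ends data collection when the infant is transferred, the family moves, or the mother withdraws one member, although some of those 3-month outcomes could still be obtained

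*Protocol*

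**What the plan says.** Protocol Section 14.0 describes when "subjects will be withdrawn from the research without their consent, including stopping participation for safety reasons". Two of the listed circumstances are "Mother and infant move away from the study site" and "Infant is transferred to another facility". Neither carries a condition such as being unable to attend, and no follow-up is described after either event.

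The same section has a prompt on voluntary withdrawal that asks how partial withdrawal with continued collection will be handled. The answer is that if the mother asks to withdraw either herself or the infant, "they will both be removed from the study without further data collection".

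Three other provisions bear on this:

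- Section 4.0 names two primary outcomes, the infant's 25(OH)D at 3 months and "Mother total circulating 25(OH)D concentration at 3 months". Maternal and infant serum calcium and the maternal urine calcium/creatinine ratio, at the start and at months 1 to 3, are safety endpoints.
- Section 7.0: "Following discharge, study visits will either be conducted in infant High-Risk Clinic or the Research Nexus clinic".
- Section 15, item 3, on unexplained elevated levels: "the patient will be withdrawn from supplementation but will continue to be monitored".

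**The concern.** Section 14.0 treats three different events as one: leaving the inpatient unit, stopping the assigned regimen, and ending data collection. Only the third loses the outcome, and the first two do not require it.

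The mother's 3-month value comes from her own blood, so the infant's location has no bearing on whether it can be drawn. A transferred infant who has since gone home can attend the same clinics as any other discharged infant. Stopping collection in these cases gives up 3-month efficacy and safety data in a trial of 50 dyads.

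Transfer happens after randomisation, which takes place 3 to 7 days after delivery, and it plausibly reflects the infant's clinical course (an assumption; the protocol does not say so). The dyads left at 3 months may then be a selected set. Two things are at stake: lost precision, which can be sized only for an assumed loss, and possible selection, which cannot be sized from the document.

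**Working it through.** **1. Which outcomes the rules lose, and whether they could be obtained**

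| Event in Section 14.0 | Mother's 3-month outcome | Infant's 3-month outcome |
|---|---|---|
| Infant transferred, discharged before month 3 | Obtainable; her own sample | Obtainable if the infant attends an on-site clinic |
| Infant transferred, still hospitalised elsewhere at month 3 | Obtainable | Not obtainable under the present set-up |
| Family moves | Only if they can travel | Only if they can travel |
| Mother withdraws one member | Obtainable if she stays in and consents | Obtainable if the infant stays in and she consents |

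The rules stop collection in all four rows. The loss is avoidable in the first row, in the maternal cell of the second, in an unknown part of the third, and in the fourth where consent stands.

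**2. The plan's own power figure**

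Inputs from Section 12.0: f = 0.834, two groups, correlation 0.5, ε = 1, α = 0.05. The number of measurements m is not printed. Numerator df = (2 − 1)(m − 1) = 2 gives m = 3.

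- λ = f²·N·m/(1 − ρ) = 0.834² × 6 × 3/0.5 = 25.040
- Denominator df = (6 − 2)(3 − 1) = 8; critical F = 4.45897
- Power = 0.96206

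This matches the printed output (total N = 6). Section 6.0 enrols 50 dyads, 25 per arm.

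**3. Effect of loss on the 3-month comparison of means**

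The protocol states no loss rate. Losses of 20% and 40% from any cause are assumed. Half-width in SD units = t(0.975, 2n − 2) × √(2/n). Power is two-sided at 5%, by noncentral t with noncentrality d√(n/2).

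| n per arm | Assumed loss | Half-width (SD) | d detectable with 80% power | Power, d = 1.668 | Power, d = 0.8 | Power, d = 0.5 |
|---|---|---|---|---|---|---|
| 25 | 0% | 2.0106 × 0.2828 = 0.57 | 0.81 | 0.9999 | 0.79 | 0.41 |
| 20 | 20% | 2.0244 × 0.3162 = 0.64 | 0.91 | 0.999 | 0.69 | 0.34 |
| 15 | 40% | 2.0484 × 0.3651 = 0.75 | 1.06 | 0.993 | 0.56 | 0.26 |

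The value d = 1.668 is the planning effect printed in Section 12.0. The values 0.8 and 0.5 are illustrative.

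**4. When loss would bias the arm comparison**

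Let w be the fraction lost in an arm and δ the amount, in SD, by which retained subjects differ from lost ones. The complete-case difference shifts by w_B·δ_B − w_A·δ_A.

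- Same w and same δ in both arms: the shift is zero.
- Loss differing by 20 percentage points with a common δ of 0.25 to 1.0 (assumptions): 0.20 × 0.25 = 0.05 SD to 0.20 × 1.0 = 0.20 SD. On the pooled V4 SD, √((28.19² + 45.88²)/2) = 38.08, that is 1.9 to 7.6 in the table's units.

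Nothing in the protocol fixes w or δ in either arm, so these figures only illustrate.

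**The case against.** The strongest reply is that the trial has ample reserve. The protocol's calculation needs 6 subjects, 50 dyads are enrolled, and power at the planning effect stays at 0.993 with 40% lost. That stands, and a reader who inferred that these rules leave the trial underpowered on its own terms would be wrong. It does not remove the loss of precision. The power table does not say whether its values are maternal or infant, and Section 15 reports no infant 25(OH)D difference between arms in the earlier trial. The margin for the infant outcome may therefore be much smaller.

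A second reply is that the rule is the same in both arms, so it need not bias the comparison. That also stands. A reader might infer that selective attrition will distort the treatment effect, but the document gives no mechanism for differential transfer and no rate. What is left without one is a question of whom the completers represent.

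Third, Section 14.0 could be read as discarding data already collected, or as removing both members whenever either leaves for any reason. Neither reading is supported. Only further collection stops, and the explicit rule removing both covers a request by the mother.

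Fourth, the intervention works through the pair: Group B infants receive placebo drops and rely on the mother's milk. That is a reason why the regimen may end when one member leaves. It is not a reason to stop measuring the other.

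Finally, monitoring and dispensing assume attended visits. Continued follow-up therefore raises a question about study product that Section 14.0 does not answer. This objection stands and is carried into the fix.

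**Conclusion.** The point holds as a weakness in a stated rule, worth correcting because correction is cheap. Followed as written, Section 14.0 gives up 3-month primary and safety outcomes that are obtainable in some dyads, most clearly the mother's own 25(OH)D after her infant is transferred.

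The number of dyads affected is unknown. If total loss from any cause reached 20% or 40%, the half-width would widen from 0.57 SD to 0.64 or 0.75 SD. Only part of that would be due to these rules, and only part of that part would be recovered by changing them. Bias in the arm comparison is possible but neither its direction nor its size can be derived. Power at the planning effect is not in question.

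The protocol already applies the sounder principle for data in Section 15, where stopping supplementation and stopping observation are kept apart.

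**What to change.** Amend Section 14.0 to say that:

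- transfer of the infant or a family move does not by itself end participation in data collection;
- the mother's scheduled visits continue to be offered, as do the infant's remaining scheduled visits at the on-site clinics whenever attendance is possible;
- withdrawal of one member does not end collection on the other where the mother's consent stands.

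Whether study product continues while infant visits are missed is for the sponsor to settle. Section 14.0 must be reconciled with the monthly safety measurements in Section 4.0, the monitoring rule in Section 15 and the dispensing and bottle checks in Section 18.0. The exit rule "If mother had baseline hypercalcemia or hypercalciuria or baby had hypercalcemia, they would exit the study" should be reconciled with the continued monitoring in Section 15 at the same time.

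The cost is protocol and consent wording, some effort to keep in contact, and some outcomes measured off the assigned regimen. No visits are added to the schedule. Families who have moved far away, and infants still hospitalised elsewhere at 3 months, may still be lost.
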